**9.5.6.4. Statistical Methods for Sub-Study****Safety Analysis:**

Summaries of AESIs will include:

- Treatment-emergent AESIs presented by AESI category, high-level term, and PT
- The number (n) and proportion (%) of patients with at least 1 treatment-emergent AESI by AESI category, high-level term, and PT
- Exposure-adjusted treatment-emergent AESIs presented by AESI category, high-level term, and PT

Summaries of all TEAEs will include:

- The number (n) and proportion (%) of patients with at least 1 TEAE by SOC and PT
- The number (n) and proportion (%) of patients with at least 1 SAE by SOC and PT
- TEAEs by severity (according to the grading scale outlined in Section 7.3.1), presented by SOC and PT
- TEAEs by relationship to treatment (related, not related), presented by SOC and PT
- TEAEs leading to permanent treatment discontinuation presented by SOC and PT

Deaths and other SAEs will be listed and summarized.

Treatment-emergent adverse events occurring before and after switching to the new dupilumab drug product will be summarized and listed separately using the SAF of the sub-study.

**PK Analysis:**

Trough concentrations of dupilumab will be summarized using descriptive statistics at each sampling time point including n, mean, median, standard deviation, geometric mean (as appropriate), coefficient of variation (if appropriate), and minimum and maximum values.

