### 2.3. Sub-Study Objectives

The primary objective of the sub-study is to assess the safety of the new dupilumab drug product in adult patients with AD after switching from the current dupilumab drug product.

The secondary objectives of the sub-study are to evaluate systemic exposure and immunogenicity of the new dupilumab drug product in adult patients with AD.

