#### **Sub-Study:**

Approximately 50 patients who are participating in the current study and have not completed the end of treatment visit (ie, visit 44) prior to the implementation of amendment 10 will be invited to participate in the sub-study. After providing signed informed consent, eligible patients will enter the sub-study at either visit 41, 43, or 44 of the main study and have study treatment switched from the current dupilumab drug product to the new dupilumab drug product at sub-study visit 1a.

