**6.2.6.1. Sub-Study Visit 1a/Day 1a/Week 0a ( $\pm 3$  days)**

Note: This visit should occur 14 days ( $\pm 3$  days) after the previous dose of current dupilumab drug product. Although, the protocol allows for a window of  $\pm 3$  days, the sponsor recommends a window  $\pm 1$  day for sub-study visit 1a after the previous dose of the current dupilumab drug product is administered.

Any redundant procedures between the main study (eg, visit 41, 43, or 44) and the sub-study (eg, visit 1a) will only be performed once.

The following information will be collected:

- Sign informed consent for sub-study
- Inclusion/exclusion criteria for switching to the new dupilumab drug product treatment (see Section 4.2.4)
- Concomitant medications/procedures
- AEs

The following procedures and assessments will be conducted:

- Weight
- Vital signs (heart rate, blood pressure, body temperature, and respiration rate)
- Ophthalmology exam (select sites and patients)
- IGA
- EASI
- Study drug dispensation/accountability
- If needed, counsel patient on proper dosing diary completion/reporting of each dose of study drug that is administered outside of the clinic
- Patient assessment of pruritus intensity via IVRS/IWRS (weekly)
- Laboratory samples:
  - Hematology w/differential
  - Serum chemistry
  - Urine pregnancy test– for women of childbearing potential
  - Drug concentration sample
  - ADA sample
- Administer study drug (new dupilumab drug product)
  - Monitor the patient for a minimum of 30 minutes after the SC injection: in addition to the predose assessments, vital signs and AE assessments will be done at 30 ( $\pm 10$ ) minutes post-injection

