#### Secondary Endpoints

- Trough concentrations ( $C_{\text{trough}}$ ) of functional dupilumab in serum before and after switching to the new dupilumab drug product
- Incidence of treatment-emergent ADA response in patients receiving the new dupilumab drug product

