**9.5.6.1. Statistical Hypothesis for the Sub-Study**

There is no statistical hypothesis for the sub-study.

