**9.5.6.2. Justification of the Sub-Study Sample Size**

No formal sample size or power calculations were performed for the sub-study.

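### Sub-study troughs are tabulated by time point only, so the before/after endpoint has no within-patient ratio, no interval and no guaranteed common set of patients

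*Protocol*

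**What the plan says.** **Objective and endpoint.** Protocol Section 2.3 includes among the secondary aims to "evaluate systemic exposure and immunogenicity of the new dupilumab drug product". Section 8.2.3 turns the exposure part into a secondary endpoint: trough concentrations "of functional dupilumab in serum before and after switching to the new dupilumab drug product".

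**Sampling.** Section 6.2.6.1 lists a "Drug concentration sample" at visit 1a (week 0a), and Section 6.2.6.3 lists another at visit 3a (week 12a). Table 8 has both drawn before that day's injection. The first is thus a trough on the current product and the second a trough on the new one. Section 6.2.6.4 adds a week 24a sample, but only for patients who switched at visit 41.

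**Analysis.** Under PK Analysis, Section 9.5.6.4 says: "Trough concentrations of dupilumab will be summarized using descriptive statistics at each sampling time point". The listed statistics are n, mean, median, SD, geometric mean and coefficient of variation where suitable, minimum and maximum. Section 9.5.6.3 admits a patient to the PK population on one qualified concentration at any time in the sub-study.

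**Framework.** Section 4.1 plans about 50 patients. Section 9.5.6.1 says "There is no statistical hypothesis for the sub-study", and Section 9.5.6.2 says "No formal sample size or power calculations were performed for the sub-study".

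**The concern.** The endpoint sets a value before the switch against a value after it in the same person, and the sampling schedule supplies that pair. Two separate rows of summary statistics do not use it. A reader of the table can form a ratio of geometric means but cannot say how well about 50 patients determine it. Nor can the reader tell whether a ratio near 1 reflects little change in everyone or offsetting rises and falls. If some patients lack one of the samples, a comparison of rows also mixes the product change with a change in who was measured.

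The same section does better by the efficacy endpoints, which are only exploratory in the sub-study: it plans absolute and percentage change from baseline for the continuous ones. The secondary PK endpoint gets no equivalent.

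**Working it through.** **1. Does any other text supply a paired analysis?**
- Protocol Section 9.5.6 applies Sections 9.5.2.1 to 9.5.2.4 and 9.5.3 to the sub-study. It does not cite 9.5.4, where an optional mixed model for steady-state troughs appears for the main study.
- The ADA paragraph of 9.5.6.4 defers further detail to the SAP. The PK paragraph does not.
- The SAP supplied is version 2.0, written to amendments 6, 7 and 8 (SAP Section 1.2.4). The sub-study arrived with amendment 10, so this SAP does not cover it.

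Nothing in the two documents pre-specifies a within-patient ratio or an interval.

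**2. What the planned table can and cannot give.** Let x and y be a patient's log troughs at weeks 0a and 12a.
- Complete pairs: mean(y − x) = mean(y) − mean(x). The ratio of the two geometric means equals the geometric mean of the individual ratios, so the point estimate is available wherever geometric means are reported.
- Precision: Var(y − x) = s_x² + s_y² − 2·r·s_x·s_y. Row-by-row statistics carry no information on r, so neither the standard error of the ratio nor the spread of individual ratios can be recovered from the table.
- Incomplete pairs: log(row ratio) = mean(y − x) in patients with both samples + [mean(x) in those patients − mean(x) in everyone sampled at 0a]. The bracket has nothing to do with the product. Illustration (assumed): 45 of 50 have both samples, and the other 5 have week 0a log troughs lower by 0.6 on average. The bracket is (5/50) × 0.6 = 0.06, a factor of exp(0.06) = 1.06.

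**3. Size of the precision question.** The plan states no precision figure to reproduce. Inputs: n = 50 (Protocol Section 4.1); log-scale SD s of 0.5 to 0.8 and within-patient correlation r of 0.5 to 0.8, **both assumed and in neither document**. 95% half-widths on the log scale:
- rows read as independent samples: 1.96·s·√(2/50)
- paired: 1.96·s·√(2(1 − r)/50)

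Worked case, s = 0.6 and r = 0.7: 1.96 × 0.6 × 0.2 = 0.235, factor exp(0.235) = 1.27; and 0.235 × √0.3 = 0.129, factor exp(0.129) = 1.14.

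| s | independent rows | paired, r = 0.5 | paired, r = 0.7 | paired, r = 0.8 |
|---|---|---|---|---|
| 0.5 | 1.22 | 1.15 | 1.11 | 1.09 |
| 0.6 | 1.27 | 1.18 | 1.14 | 1.11 |
| 0.8 | 1.37 | 1.25 | 1.19 | 1.15 |

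Entries are the factors by which the ratio is multiplied and divided to give its limits.

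**4. Sensitivity.** The paired half-width is √(1 − r) times the other. At r = 0.3 that is √0.7 = 0.84, and at r = 0 there is no gain. A second calculation used t quantiles, 90% intervals and s = √ln(1 + CV²). At CV 60% and 50 pairs it gives 1.20 for independent rows, against 1.14, 1.11 and 1.09 paired at r = 0.5, 0.7 and 0.8. With 40 pairs and r = 0.7 it gives 1.23 against 1.12.

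**The case against.** The other side has a good case.

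- **The plan does what its endpoint says.** The endpoint is troughs before and after, not a ratio. Protocol Section 1.2.3 rests product comparability on quality testing and protein characterization and promises only that before/after PK results will be summarized and listed. With no hypothesis and no margin, nothing obliges an interval. This stands: the table is incomplete as evidence on exposure, but it breaks no rule of the plan.
- **The pairing is not thrown away.** A reader might infer from the by-time-point wording that the paired information is lost. The documents do not support that: individual values are to be listed, so ratios can be rebuilt. What is missing is a pre-specified choice of pairs, scale and exclusions.
- **No unpaired interval is planned.** A reader might take 1.27 against 1.14 as the plan's loss. It is not: the plan gives no interval at all, and the wider figure arises only if someone treats the rows as independent samples.
- **The gain is assumed.** This stands as to size. The direction holds for any appreciable positive correlation.
- **Loss of samples over 12 weeks may be small, and n is shown for each row.** Fair, but n shows that the rows differ without removing the difference. The week 24a row is a subset by design.
- **A later SAP may cover it.** Protocol Section 9 calls itself the basis for a SAP covering the sub-study, to be final before database lock. The finding is therefore limited to the documents in hand.

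**Conclusion.** The point holds as a gap in informativeness and pre-specification. For a secondary endpoint defined by before and after values in the same patients, the documents plan no within-patient ratio, no measure of its precision, no description of individual ratios and no common set of patients. The planned point estimate is not wrong: with complete pairs it equals the paired one.

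If troughs vary and correlate as assumed above, 50 pairs would fix the ratio to within about x/÷ 1.09 to 1.25 at 95%. That is useful information which the planned table cannot show. At low correlation the precision argument fades. The arguments from individual spread and from a common set of patients do not depend on the correlation.

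A reader might go further and call the sub-study an underpowered equivalence comparison. The documents do not support that, since they set no hypothesis, margin or power. Label: cheap improvement.

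**What to change.** Add to Protocol Section 9.5.6.4, or to the sub-study SAP before database lock:

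1. For patients with qualified pre-dose troughs at weeks 0a and 12a, report the geometric mean of the within-patient ratio (12a/0a) with a 90% or 95% confidence interval from the paired log differences. Name the level in advance and present the interval as descriptive.
2. Report the distribution of individual ratios and the number of complete pairs.
3. Do the same for 24a/0a in patients who switched at visit 41.
4. Keep the by-time-point table.

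No new data are needed, but the change is not quite free, because short rules must be written first:

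- **Values below the lower limit of quantitation.** SAP Section 5.9 sets these to zero for the main study. A zero cannot enter a log ratio, and it would also break the geometric mean already planned.
- **Off-schedule troughs.** Visits 1a and 3a each have a ±3-day window, so state which samples qualify and how the rest are treated.
- **Missed doses.** The compliance rule in Section 4.2.4.1 covers injections before week 0a only. State how a week 12a trough after missed injections is handled.

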**ADA Analysis:**

Listings of ADA positivity, treatment-emergent ADA, and titers presented by patient and time point will be provided. Incidence of treatment-emergent ADA will be assessed as absolute occurrence (N) and percent of patients (%) grouped by ADA titer level. The ADA variables will be summarized and listed by before (sub-study week 0a) and after switching to the new dupilumab drug product using the SAF of the sub-study. Additional details of ADA data analysis for the sub-study will be provided in the SAP.

**Efficacy Analysis:**

The efficacy endpoints will be summarized using descriptive statistics. These include the proportions for categorical endpoints and basic statistics of original, absolute, and percentage change from baseline for continuous endpoints.

All observed data will be used for analysis.

All efficacy endpoints will be summarized by before and after switching to the new dupilumab drug product using the SAF of the sub-study.

**9.6. Additional Statistical Data Handling Conventions**

The following analysis and data conventions will be followed:

Definition of baseline:

- The baseline assessment will be the latest, valid predose assessment available.

General rules for handling missing data:

- If the start date of an AE or concomitant medication is incomplete or missing, it will be assumed to have occurred on or after the intake of study medication, except if an incomplete date (eg, month and year) clearly indicates that the event started prior to treatment. If the partial date indicates the same month or year of the intake of study medication date, then the start date by the study medication intake date will be imputed, otherwise, the missing day or month by the first day or the first month will be imputed.
- No imputations for missing laboratory data, electrocardiogram data, vital sign data, or physical examination data will be made.

Visit windows:

- Assessments taken outside of protocol allowable windows will be displayed according to the CRF assessment recorded by the investigator.

Unscheduled assessments:

- Extra assessments (laboratory data or vital signs associated with non-protocol clinical visits or obtained in the course of investigating or managing AEs) will be included in listings, but not summaries. If more than 1 laboratory value is available for a given visit, the first observation will be used in summaries and all observations will be presented in listings.

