**6.2.2.8. Visit 9/Day 113/Week 16 (+/-3 Days)**

The following information will be collected:

- Concomitant medications/procedures
- AEs

The following procedures and assessments will be conducted:

- Vital signs (heart rate, blood pressure, body temperature, and respiration rate)
- Ophthalmology exam (select sites and patients)
- IGA
- EASI
- Patient assessment of pruritus intensity via IVRS/IWRS (weekly)
- Laboratory samples:
  - Hematology w/differential
  - Serum chemistry
  - Urine pregnancy test – for women of childbearing potential
- If needed, counsel patient on proper dosing diary completion/reporting of each dose of study drug that is administered outside of the clinic
- Study drug dispensation/accountability
- Administer study drug

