**6.2.2.16. Visit 17/Day 337/Week 48 (+/-3 Days)**

The following information will be collected:

- Concomitant medications/procedures

The following procedures and assessments will be conducted:

- Weight
- Vital signs (heart rate, blood pressure, body temperature, and respiration rate)
- IGA
- EASI
- Ophthalmology exam (select sites and patients)
- Patient assessment of pruritus intensity via IVRS/IWRS (weekly)
- Administered only to the subset of patients who speak fluently the language in which the questionnaire can be translated:
  - POEM
  - DLQI
  - EQ-5D

- Laboratory samples:
  - Hematology w/differential
  - Serum chemistry
  - ADA sample
  - Drug concentration sample
  - Urine pregnancy test – for women of childbearing potential
- If needed, counsel patient on proper dosing diary completion/reporting of each dose of study drug that is administered outside of the clinic
- Study drug dispensation/accountability
- Administer study drug

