**6.2.2.23. Visit 24/Day 701/Week 100 (+/-3 Days)**

The following information will be collected:

- AEs

The following procedures and assessments will be conducted:

- Weight
- Vital signs (heart rate, blood pressure, body temperature, and respiration rate)
- IGA
- EASI
- Administered only to the subset of patients who speak fluently the language in which the questionnaire can be translated:
  - POEM
  - DLQI
  - EQ-5D
- Patient assessment of pruritus intensity via IVRS/IWRS (weekly)
- Laboratory samples:
  - Hematology w/differential
  - Serum chemistry
  - Urine pregnancy test – for women of childbearing potential
  - Drug concentration sample
  - ADA sample
- If needed, counsel patient on proper dosing diary completion/reporting of each dose of study drug that is administered outside of the clinic
- Study drug dispensation/accountability
- Administer study drug

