#### **6.2.9. Unscheduled Visits**

All attempts should be made to keep patients on the study schedule. Unscheduled visits may be necessary to repeat testing following abnormal laboratory results, for follow-up of AEs, or for any other reason, as warranted. During an unscheduled visit, any of the study procedures noted may be performed, but not all are required.

The following information will be collected:

- Study drug accountability
- Concomitant medications/procedures
- AEs

The following procedures and assessments will be conducted:

- Weight
- Vital signs (heart rate, blood pressure, body temperature, and respiration rate)
- Ophthalmology exam (select sites and patients)
- IGA
- EASI
- Patient assessment of pruritus intensity via IVRS/IWRS (weekly) (not to be repeated if performed on the patient's weekly schedule)
- Laboratory samples:
  - Hematology w/differential
  - Serum chemistry
  - Urine pregnancy test – for women of childbearing potential (to be performed only if coincides with the patient's weekly schedule, or with the monthly pregnancy test)
  - HIV screening

- HBsAg, HBcAb, hepatitis C antibody
- Drug concentration sample
- ADA sample

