##### Laboratory Tests

Laboratory test results will be summarized by baseline and change from baseline to each scheduled assessment time with descriptive statistics.

Number and percentage of patients with a treatment-emergent potentially clinically significant value (PCSV) will be summarized for each clinical laboratory test.

Shift tables based on baseline normal/abnormal and other tabular and graphical methods may be used to present the results for laboratory tests of interest.

Listings will be provided with flags indicating the out of laboratory range values.

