5.8. Analysis of Safety Data

The summary of safety and tolerance will be performed for all patients in SAF.

The safety analysis will be based on the reported AEs, clinical laboratory evaluations, physical examination, vital signs, and 12-lead ECG.

Thresholds for treatment-emergent Potentially Clinically Significant Values (PCSV) in laboratory variables, vital signs and ECG are defined in [Appendix 10.3](#). The baseline when determining treatment-emergent PCSV refers to the baseline value of current study.

The time interval to detect any event or abnormality is between the first injection of study medication and EOS.

Subgroups are defined by key baseline factors recorded on the CRF and listed to be considered for safety analyses:

- Age group (≥ 18 - <40 , ≥ 40 - <65 , ≥ 65)
- Sex (Male, Female)
- Ethnicity: Hispanic or Latino (no/yes)
- Race (White, Black or African American, Asian, Other)
- Duration of AD based on data from parent studies (< 26 years, ≥ 26 years)
- Baseline weight group (<70 kg, ≥ 70 - <100 kg, ≥ 100 kg)

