Analysis visit windows will be applied to map all study scheduled visits except extension end of study visit or end of study visit under protocol amendment 7 or 8, based on the study day. Data collected at extension end of study visit or end of study visit under protocol amendment 7 or 8 will be summarized using the nominal visit (i.e. extension end of study visit or end of study visit).

Visit	Target Day	Analysis Visit Window Based on Study day*
Screening	<1	<1
Baseline	1	1
Week 1	8	[2,11]
Week 2	15	[12,18]
Week 3	22	[19, 25]
Week 4	29	[26, 43]
Week 8	57	[44, 71]
Week 12	85	[72, 99]
Week 16	113	[100, 127]
Week 20	141	[128, 155]

Visit	Target Day	Analysis Visit Window Based on Study day*
Week 24	169	[156, 183]
Week 28	197	[184, 211]
Week 32	225	[212, 239]
Week 36	253	[240, 267]
Week 40	281	[268, 295]
Week 44	309	[296, 323]
Week 48	337	[324, 351]
Week 52	365	[352, 393]
Week 60	421	[394, 449]
Week 68	477	[450, 505]
Week 76	533	[506, 561]
Week 84	589	[562, 617]
Week 92	645	[618, 673]
Week 100	701	[674, 729]
Week 108	757	[730, 785]
Week 116	813	[786, 841]
Week 124	869	[842, 897]
Week 132	925	[898, 953]
Week 140	981	[954, 1009]
Week 148	1037	[1010, 1065]
Week 156	1093	[1066, 1149]
Week 172	1205	[1150, 1261]
Week 188	1317	[1262, 1373]
Week 204	1429	[1374, 1485]
Week 220	1541	[1486, 1597]
Week 236	1653	[1598, 1709]
Week 252	1765	[1710, 1793]
End of study	1821	>=1794

*study day is calculated relative to the date of first study drug injection.

In general, the following order will be used to select the record for analysis at given visit:

1. Scheduled visit
2. Early termination (ET) or end of study (EOS), whichever comes first if scheduled visit not available
3. Unscheduled visit if both scheduled visit and ETV/EOT/EOS are not available

For the multiple measurements of the same test in the same window, the following rules will be used to pick up the analysis value:

- If multiple valid values of a variable within an analysis visit window, the closest from the target study day will be selected.
- If the difference is a tie, the value after the targeted study day will be used.
- If multiple available values of a variable exist within a same day, then the first value of the day will be selected.

Analysis visit window mapping for weekly pruritus NRS

For the weekly pruritus NRS collected via IVRS, the following analysis visit windows will be used based on the study day:

Visit	Target Day	Analysis Visit Window Based on Study day*
Screening	<1	<1
Baseline	1	1

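### Protocol 9.6 keeps unscheduled and AE work-up values out of every summary, PCSV counts included; the SAP leans the other way but never says which values are counted

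*Protocol*

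**What the plan says.** Protocol 9.6, under unscheduled assessments, covers laboratory data and vital signs from visits outside the protocol schedule or "obtained in the course of investigating or managing AEs) will be included in listings, but not summaries". It makes no exception for any type of summary. Its next sentence adds that when a visit has more than one laboratory value, the first is summarised and the others are only listed.

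Protocol 9.5.2.2 (Laboratory Tests) states: "Number and percentage of patients with a treatment-emergent potentially clinically significant value (PCSV) will be summarized for each clinical laboratory test". The PCSV count is therefore a summary in the protocol's own terms. For vital signs the protocol plans only descriptive statistics; the vital-sign PCSV count comes from SAP 5.8.3.

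The SAP reads differently:
- SAP 5.8: "The time interval to detect any event or abnormality is between the first injection of study medication and EOS".
- SAP 5.8.2 counts patients with treatment-emergent PCSVs, and patients who move from normal to abnormal, over the study and not by scheduled visit.
- SAP 6.4 makes the by-visit windows exhaustive so that unscheduled values may be summarised. It then keeps one record per window, with the unscheduled value last in order: "Unscheduled visit if both scheduled visit and ETV/EOT/EOS are not available".

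SAP 1.2.3, which lists modifications from the protocol's statistical section, says nothing on this. Protocol section 9 describes itself as the basis for the SAP. Amendment 10 edited the protocol to agree with SAP version 2.0 on time-to-event endpoints and left the 9.6 rule in place.

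**The concern.** Keeping unscheduled values out of by-visit means is sensible, because those values are drawn selectively. A count of patients who ever cross a safety limit is a different quantity: it asks whether a limit was crossed at any time, and selective sampling is no reason to ignore a crossing that was observed. The excluded values are also likely to be informative. Protocol 6.2.9 explains: "Unscheduled visits may be necessary to repeat testing following abnormal laboratory results, for follow-up of AEs, or for any other reason, as warranted". In the main study, hematology and chemistry are not scheduled at early termination or end of study, so for a patient who leaves between scheduled draws an unscheduled sample may be the only late laboratory result.

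Long-term safety is the primary objective. At stake is whether a laboratory value beyond a PCSV limit that was drawn and recorded reaches the PCSV table or only a listing. Two programmers working faithfully, one from the protocol and one from the SAP, could report different percentages.

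**Working it through.** The documents give no figure on this point, so there is none to reproduce. The check has three parts.

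**1. The texts side by side**

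| Situation | Protocol 9.6 with 9.5.2.2 | SAP |
|---|---|---|
| Only value beyond the limit is from an unscheduled visit or AE work-up | Listed, not counted | Inside the 5.8 interval and during the study (5.8.2): counted on the natural reading, but not stated |
| Repeat at the same visit is worse than the first value | First value used | Same natural reading; if the 6.4 record selection were applied, the first value of the day would be used |
| Sub-study (amendment 10) | Same rule: 9.5.6 points back to 9.5.2.2 | No text: SAP 2.0 is based on amendments 6 to 8 |

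The 6.4 selection concerns by-visit analysis, but no SAP sentence says that PCSV counts bypass it. Where a window holds several values, it chooses by visit type and then closeness to the target day, never by worst value.

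Even if 6.4 were applied to PCSVs, it would not reproduce the protocol rule. In the amendment 7/8 table, the windows that contain a scheduled laboratory draw are days 100–127, 324–351, 674–729, 1010–1065, 1374–1485 and 1794–1821. That is 28 + 28 + 56 + 56 + 112 + 28 = 308 of the 1,820 days from day 2 to day 1821. The other 1,512 days (1,512/1,820 = 83%) lie in windows with no scheduled draw, where an unscheduled value could be used. In the week-148 table it is 28 + 28 + 56 + 84 = 196 of 1,092 days, leaving 896 (82%). These are shares of days, not of extra samples.

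**2. How sparse the scheduled draws are**

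Under the current protocol (6.2.2.8, 6.2.2.16, 6.2.2.23, 6.2.3, 6.2.4, 6.2.5), on-treatment hematology and chemistry fall at weeks 16, 48, 100, 148, 204 and 260. Counting from baseline, the intervals are 16, 32, 52, 48, 56 and 56 weeks.

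Assume an abnormality of length d weeks with onset uniform over L weeks. The documents give no duration, so d is an assumption. While d does not exceed the shortest interval (16 weeks), the share of episodes that contain a scheduled draw is (number of draws × d)/L.

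| d (weeks) | L = 260, 6 draws | L = 148, 4 draws |
|---|---|---|
| 4 | 24/260 = 9.2% | 16/148 = 10.8% |
| 8 | 48/260 = 18.5% | 32/148 = 21.6% |
| 12 | 72/260 = 27.7% | 48/148 = 32.4% |

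This describes the schedule. It is not the effect of the 9.6 rule, which acts only on extra values that were actually drawn. An episode with no draw at all is missed under any rule.

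**3. What one patient is worth**

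The documents give no rate of extra draws, so the number of patients affected cannot be derived. Each patient whose only PCSV is on an extra value moves a percentage by about 1/50 = 2 points in the sub-study (about 50 planned) and about 1/2,678 = 0.04 points in the main study (2,678 enrolled, SAP 2.2). Actual denominators will be somewhat smaller.

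**The case against.** The strongest reply is that the SAP governs the analysis and already leans the right way. Its detection interval runs from first injection to end of study, its PCSV count is not tied to scheduled visits, and it makes unscheduled values eligible for by-visit summaries. On that view 9.6 is a leftover sentence and nothing is lost in practice. Much of this stands. It is why the defect is an unreconciled conflict, not proof that the values will be dropped. It does not close the matter: the SAP neither declares a departure from 9.6 nor says which values feed the PCSV count, and it does not reach the sub-study.

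A second reply is that laboratory abnormalities are also captured as adverse events. Protocol 7.2.5 makes an abnormal result reportable when it comes with symptoms, needs further diagnostic testing or intervention, or changes dosing or other treatment, and such events enter the TEAE tables. Unscheduled repeats also often follow a value already eligible for the PCSV count. Both points stand, but the cover is partial. The same section says that repeating an abnormal test without those conditions does not make it an AE. An asymptomatic value beyond a PCSV limit, found at an unscheduled visit and merely repeated, would be in neither the TEAE tables nor the protocol's PCSV count. All values remain in the listings.

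Third, the sparse spacing does not describe all the data. Before amendment 6, more than 1,400 patients had followed a more intensive schedule, and the sub-study draws at weeks 0a and 12a and at end of study. That is correct, and it limits how far the 9% to 28% range applies.

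**Conclusion.** The point holds as an inconsistency with a direction. Read literally, protocol 9.6 with 9.5.2.2 takes unscheduled and AE work-up values, and worse repeats at a visit, out of the treatment-emergent PCSV counts, and this can only lower the number of patients counted. SAP 5.8, 5.8.2 and 6.4 point the other way without saying so expressly, and for the sub-study the protocol rule stands alone in the documents supplied.

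The size of the undercount is not quantifiable from the documents. The 9% to 28% range rests on the current schedule, an assumed duration of 4 to 12 weeks and uniform onset, and it measures the spacing of the draws.

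A reader might infer that transient laboratory toxicity cannot be counted at all, or that the rule removes the 72% to 91% of episodes (100% minus 27.7% and 9.2%) that meet no scheduled draw. The documents support neither. The SAP leans towards counting extra values, 7.2.5 keeps many such abnormalities in the TEAE tables, and most of that gap would exist only where nobody drew blood. A reader might also infer a bias towards no effect. In a single-arm study with no hypothesis, this can mean no more than a possible undercount in one of several laboratory summaries; the primary endpoint is TEAEs.

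**What to change.** In protocol 9.6, limit the listings-only rule and the first-value-per-visit rule to by-visit descriptive statistics. In 9.6 and in SAP 5.8.2 and 5.8.3, add a sentence such as: Treatment-emergent PCSV counts and normal-to-abnormal counts use all post-baseline values, scheduled or unscheduled, including repeats. Make sure the analysis plan for the sub-study carries the same sentence. If the protocol is not to be amended again, put the rule in the SAP and list it in SAP 1.2.3 as a departure from 9.6.

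No new data are needed. The cost is a few sentences, a small programming change and slightly higher PCSV percentages. By-visit tables keep their windowed values.
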